The investigators hypothesise that LUS can detect lung injury after lung resection surgery. The primary objective of the study is to assess changes in lung aeration after lung resection with mLUSS. Secondary objectives are, first, to describe LUS findings after lung resection surgery, second, to assess the ability of mLUSS to detect oxygenation changes after lung resection and third, to compare the behaviour of inflammatory mediators in plasma with mLUSS changes.

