## **Outcome measures**

## 1. Primary outcome measure

Title: change in mLUSS after lung resection. Description: the modified lung ultrasound score (mLUSS) ranges 0-36; the higher the score, the less aeration (worse). Timeframe: preoperative vs immediate postoperative period vs 24 hours after surgery.

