## 1. Study groups

This is a prospective, single-centre, observational study in which 30 consecutive participants with non-small cell lung cancer scheduled for lung resection via VATS will be recruited. Participants will be divided in two groups depending on the size of the resection. First group will be resection less than lobectomy. Second group will be resection equal to or greater than lobectomy. Participants will be recruited consecutively until there are 15 patients in each group. Sample size has not been calculated, as there is no previous information on changes in lung aeration after lung resection. Sample size will be set in 28 participants, adding 5% (30 participants in total) to compensate for possible losses.

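### Does filling two groups of 15 contradict a series of 30 consecutive patients, and does it distort the primary result?

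*Protocol*

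**What the plan says.** Under Methods, 1. Study groups, and in the same words in the Detailed description, the protocol announces that "30 consecutive participants with non-small cell lung cancer scheduled for lung resection via VATS will be recruited". It then says "Participants will be divided in two groups depending on the size of the resection": less than lobectomy, and lobectomy or greater. The recruitment rule follows: "Participants will be recruited consecutively until there are 15 patients in each group".

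The total is not derived from a power calculation: "Sample size has not been calculated, as there is no previous information on changes in lung aeration after lung resection". Instead, "Sample size will be set in 28 participants, adding 5% (30 participants in total) to compensate for possible losses".

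The aim is stated without reference to the groups: "The primary objective of the study is to assess changes in lung aeration after lung resection with mLUSS". The primary outcome is likewise headed "Title: change in mLUSS after lung resection", on a score from 0 to 36, and its contrast is over time: "Timeframe: preoperative vs immediate postoperative period vs 24 hours after surgery". Neither place says whether the change is to be pooled over the two groups, stratified or reported by group.

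**The concern.** Thirty consecutive patients bring whatever mix of resections the theatre list produces. Reaching 15 in each group then requires one of two things: recruiting beyond 30, or closing the commoner group once it is full and passing over later eligible patients. The second is quota sampling, and the 30 are then consecutive only within each group.

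If that is what happens, three things could be at stake:

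- The report might claim an unrestricted consecutive series that was not obtained.
- The last recruits would all come from the rarer group, so group membership would be partly tied to calendar time.
- A simple mean over all 30 would give each group half the weight. If the mLUSS change depends on resection size and the centre's real mix is uneven, that mean would differ from the average change in the centre's patients.

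**Working it through.** **Inputs from the protocol:** 30 patients in total; 15 per group; base number 28 plus 5%; groups defined by the surgery performed. **Assumed, because the protocol gives no figure:** the share p of eligible patients in one of the two groups (0.5 to 0.8; results are symmetric in p and 1 − p), and the between-group difference D in mean mLUSS change.

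**1. The stated total.** 28 × 1.05 = 29.4 and 28 / 0.95 = 29.5. Both round up to 30, and 15 + 15 = 30. The total and the group sizes agree.

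**2. Chance that 30 unrestricted consecutive patients split 15:15.** P = C(30,15) × p^15 × (1 − p)^15. The number of consecutive eligible patients needed until both groups hold 15 was obtained by summing, over n, the probability that at least one group is still short after n patients. If full groups close, the excess over 30 is the expected number passed over.

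| Case mix (assumed) | P(15:15 in 30) | Expected eligible patients to fill both | Excess over 30 |
|---|---|---|---|
| 50:50 | 14.4% | 34.3 | 4.3 |
| 60:40 | 7.8% | 38.2 | 8.2 |
| 70:30 | 1.1% | 50.0 | 20.0 |
| 80:20 | 0.02% | 75.0 | 45.0 |

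So an unrestricted series of 30 would meet the group rule only by chance. The probability in the second column, however, tests a reading that the group rule itself rules out. If each group fills consecutively to 15 and then closes, the 15:15 split among recruits is certain by design.

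**3. Size of the pooled shift, if there is one.** An equally weighted mean differs from the case-mix mean by |p − 0.5| × D.

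- 70:30 with assumed group means 6 and 3: (0.7 − 0.5) × (6 − 3) = 0.6 points.
- 60:40 with D = 4: 0.1 × 4 = 0.4 points. 80:20 with D = 4: 0.3 × 4 = 1.2 points.
- 50:50 with any D, or any mix with D = 0: no shift.

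**4. What the shift requires.** Four conditions must hold together: full groups close; the analysis pools without weights; the change differs by resection size; and the target is the average over the centre's natural case mix. The first is the likely reading. The second and fourth are not stated in the protocol. The third is unknown, and neither the hypothesis nor the objectives assert it.

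**5. What does not depend on the mix.** Each patient serves as their own baseline. The mean change within each group, and any comparison between the groups, is the same whatever share of the centre's patients each group represents.

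**The case for a change.** The best case for acting is that both ways of reconciling the sentences cost something. If recruitment runs on until both groups have at least 15, the series stays consecutive but the total passes 30, against the stated sample size. If full groups close, the total holds but the sample is no longer one consecutive series. A statistical analysis plan cannot repair this later: if patients passed over are never logged, the case mix cannot be recovered. At 70:30 the commoner group fills after about 15 / 0.7 = 21 eligible patients, when the rarer group holds about 0.3 × 21.4 = 6, so more than half of the rarer group is enrolled afterwards. The protocol also leaves open whether patients removed for transfusion, pleurodesis or conversion to thoracotomy (Methods, section 2, on eligibility) count towards the 15.

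Part of this stands. The description as consecutive is loose if full groups close, closure is not spelled out, and a report should call the sample consecutive within resection groups. A log of eligible patients would be good practice.

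The rest carries less weight. Only closing full groups gives both 30 and 15 + 15, so a reader would arrive at that rule unaided. The calendar-time point needs a trend over the recruitment period in the within-patient change, and nothing in the protocol suggests one; until the first group fills, both accrue in parallel. The step from 28 to 30 allows for 2 losses in 30, which suggests that removed patients are covered by the allowance and not replaced. Weighting by logged case mix is not clearly better: some removals occur during or after surgery, so the eligible population in a log is not the population analysed.

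**Conclusion.** The concern does not call for a change. The arithmetic is right: an unrestricted run of 30 would split 15:15 at most 14.4% of the time. But it is aimed at a reading that the next sentences of the same section displace. Consecutive enrolment within each resection group until 15 are reached satisfies both the group rule and the total, and balanced groups are a fair choice for a small exploratory study that openly makes no sample size calculation. What remains is a clerical looseness in one word and some unstated operational detail.

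The claim of a distorted primary result is not supported. It supposes an unweighted pooled mean and a target population that the protocol does not name; whether to pool or report by group is a choice commonly left to the analysis plan, which is not at hand. The 0.6-point figure rests wholly on an assumed 70:30 mix and assumed group means, and falls to zero under an even mix or equal changes. Followed as written, the protocol yields sound within-patient and within-group mLUSS changes. This conclusion assumes that full groups close; if recruitment instead ran past 30, the series would remain consecutive and the 50:50 objection would not arise.

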#### 2. Elegibility

Inclusion Criteria:
Age > 18
ASA I-III
Non-small cell lung neoplasm
Elective lung resection
Via VATS
Under one-lung ventilation

**Exclusion Criteria:** -Pregnancy Respiratory tract infection the previous month Diagnosed pulmonary fibrosis Predicted FEV < 40% Surgery limited to biopsy Surgery that includes resection of the thoracic wall or the diaphragm Neoplasm metastasis Obesity class II or more (BMI  $\ge$  35 kg/m^2) Risk of malnutrition CONUT > 1 Hemoglobin < 10 g/dlChronic kidney failure: glomerular filtration < 60 ml/min/m^2, nephrectomy, kidney transplantation Treatment with corticosteroids or immunosuppressive agents 3 months before surgery Transfusion of blood products during the previous 10 days Heart failure (New York Heart Association Functional Class 3 or 4) during the week before surgery. Heart valve diseases over stage B of the American College of Cardiology/American Heart Association Task Force on Practice Guidelines 2014 **Diastolic dysfunction** 

Recruited participants will be excluded in the following cases:

Intraoperative or postoperative blood product transfusion (first 24 h) Pleurodesis Need to convert to thoracotomy

### 3. Study protocol

#### **Baseline characteristics**

The following demographic data will be collected: age, sex, height, weight, BMI, malnutrition universal screening tool (MUST) score and CONUT nutrition score, American society of anaesthesiologists (ASA) status, and ARISCAT score.

Information regarding comorbidities will include the following: hypertension, diabetes, myocardial ischemia, NYHA, EPOC GOLD score, asthma, obstructive sleep apnoea (OSA), smoking state and alcohol intake.

The following data regarding pulmonary function testing will be included: forced expiratory velocity (FEV1), forced vital capacity (FVC), diffusing capacity of the lungs for carbon monoxide (DLCO) and peripheral oxygen saturation (SpO2) breathing room air.

In addition to this, heart rate and median arterial pressure will be recorded.

#### **Preoperative evaluation**

This will include the following examinations (explained at the end of the protocol):

- ultrasound including lung, diaphragm and echocardiography.
- blood analysis for measurement of inflammatory mediators, as well as blood count and chemistry.
- chest X-ray

#### Anaesthesia protocol

Analgesia will be administered via a paravertebral catheter in the non-dependent hemithorax of participants undergoing a resection equal to or greater than lobectomy, with an initial dose of 0'25% levobupivacaine (0'3 ml/kg) followed by subsequent boluses of 0'25% levobupivacaine 6-10 ml every hour. Analgesia will be administered via an erector spinae single shot block in the non-dependent hemithorax of participants undergoing rection less than lobectomy, with 0'25% levobupivacaine (0'3 ml/kg) plus infiltration of the ports at the end of the procedure with levobupivacaine 0'25%. Anaesthesia will be induced with propofol (2 to 3 mg/kg) and fentanyl (2-3 mcg/kg). Neuromuscular blockade will be achieved with rocuronium (0.6 to 1 mg/kg). Orotracheal intubation will be performed with a left double-lumen tube (35 to 37 Fr in women and 39 to 41 Fr in men). Correct placement will be verified by direct visualisation with a fibreoptic bronchoscope. All patients will be managed using a Perseus ventilator (Drägerwerk). Volume-controlled ventilation will be used during two-lung ventilation (TLV) with the following parameters: tidal volume 7 ml/kg (predicted body weight); inspiratory pause 25%, positive end-expiratory pressure (PEEP) 5cmH2O; fraction of inspired oxygen (FiO2) 0.4 to 0.5; and respiratory

rate to maintain end-tidal carbon dioxide pressure (ETCO2) at 35 to 45 mmHg. Hypnosis will be maintained with sevoflurane at the necessary concentrations to maintain a bispectral index of between 40 and 60. A continuous infusion of rocuronium will be used to achieve profound neuromuscular blockade with train of four (TOF) of 0. A continuous infusion of remifentanil 0.1-0.3 mcg/kg/min will be used to achieve hemodynamic stability after having administered levobupivacaine through the paravertebral catheter, in the cases where there is a catheter. Intermittent pneumatic compression stocks and convective warming blanket will be systematically used.

OLV will be undertaken using volume-controlled ventilation and the following parameters: tidal volume 5 ml/kg (predicted body weight); inspiratory pause 25%, PEEP 5cmH2O; permissive hypercapnia; and FiO2 0.6 to 1 in order to maintain oxygen saturation (SaO2) more than 90%. A recruitment manoeuvre (RM) will be systematically performed after the initiation of OLV and the ensuing optimal PEEP will be set. Another RM will be systematically performed after recruitment manoeuvres or continuous positive airway pressure (CPAP) to the non-dependent lung will be instituted in the event of hypoxemia. Restrictive intravenous fluid therapy will be used, with fluids given at 2 ml/kg/ h in order to maintain urine output 0.5 ml/kg/h. Fluid administration will be recorded; crystalloids and colloids. Urine output, the use of diuretics (drug and dose), the estimated blood loss and overall fluid balance will also be recorded.

At baseline during TLV, at 10 min after RM in OLV and at 10 min after RM in TLV data regarding haemodynamic monitoring, ventilation and blood gas exchange will be recorded, as explained below.

The radial artery will be catheterised in all cases (FloTrac Sensor; Edwards Lifesciences Corp., Irvine, California, USA) for intraoperative monitoring of continuous cardiac index, stroke volume variation, stroke volume index and invasive arterial pressure.

Registered data regarding ventilation will be recorded as follows; FiO2; peripheral oxygen saturation (SpO2); ETCO2; tidal volume (TV); respiratory rate; peak, plateau, mean, driving and end-expiratory airway pressures; and lung compliance.

Arterial blood will be drawn for measurement of respiratory gases (pH, paO2, paCO2) and lactate.

Attending surgeon, duration of anaesthesia, total dose of opioids given, duration of surgery, extent of lymphatic resection and weight of the resected piece will also be recorded.

The intraoperative complications considered relevant for the study will be registered and include: desaturation (SpO2 < 90% more than 2 minutes), hypotension (PAS < 90 mmHg or PAM < 65 mmHg more than 3 minutes) and new onset arrhythmia (atrial fibrillation, atrial flutter, ventricular tachycardia, ventricular fibrillation). If there is need of infusion of vasoactive drugs, the drug and cumulative dose will also be registered.

At the end of the surgery, neuromuscular blockade will be reversed with sugammadex for a TOFr> 0'9 before extubation. Participants will then be transferred to the ICU or PACU with supplemental oxygen FiO2 0.4 through a venturi mask.

#### Postoperative course: Immediate postoperative period

Depending on factors related to surgery and to participants, postoperative care will take place in the ICU or PACU.

At their arrival at ICU or PACU, chest drains will be connected to aspiration -20 cmH2O, and for those participants in whom there is an indwelling paravertebral catheter, continuous infusion of levobupivacaine 0'125% at 10-12 ml/h will be used until 72 h after surgery.

Examinations will include the following (explained at the end of the protocol):

- ultrasound including lung, diaphragm and echocardiography.
- blood analysis for measurement of inflammatory mediators, as well as blood count and chemistry.
- chest X-ray

The following data will be registered: SpO2, FiO2, heart rate, median arterial pressure, analgesia using visual analogue scale (VAS) at rest and presence of air leak through chest drains.

All participants will receive supplemental oxygen FiO2 0.4 through a venturi mask at least during the first postoperative hour. 15-30 minutes after arrival at ICU, if the participant is fully awake with Glasgow comma scale (GCS) > 13, is not agitated with Richmond Agitation-Sedation Scale (RASS) -1 to +1, has adequate analgesia level VAS < 4 and SpO2  $\geq$ 97% with venturi mask FiO2 0.4, an Air-Test will be performed. Oxygen mask will be removed and participants will be left breathing room air for at least 5 min while continuously monitoring SpO2. The Air-Test will be considered positive when the recorded SpO2 is  $\leq$ 96% and negative when SpO2 is  $\geq$ 97%. The oxygen mask will be placed back whenever SpO2 falls to 92% for more than 1 min during the Air-Test. Once the Air-Test is completed an arterial blood gas analysis will be done while breathing room air. Incentive spirometry will then be started.

#### Postoperative course: 24 hours after surgery

Participants who were admitted to the ICU will be transferred to the ward as per standard practice if the postoperative course is uneventful. Before being transferred data will be recorded. For participants who were not admitted to the ICU and were transferred to the ward after PACU vigilance, the same data will be recorded.

Examinations will include the following (explained at the end of the protocol):

- ultrasound including lung and diaphragm.
- blood analysis for measurement of inflammatory mediators, as well as blood count and chemistry.
- chest X-ray

The following data will be recorded: SpO2, FiO2, heart rate, mean arterial pressure, SAPS II, presence of air leak through the chest drains, administered fluids (crystalloids, colloids and blood products), urine output, use of diuretics (drug and dose), estimated blood loss and overall fluid balance. If there has been need of infusion of vasoactive drugs, the drug and cumulative dose.

Regarding analgesia, the following data will be collected: VAS at rest and during coughing, total dose of given opioids, infusion on levobupivacaine 0'125% through paravertebral catheter.

Regarding pulmonary function, the best result of incentive spirometry (0, 1, 2 or 3 balls lifted) will be recorded and participants will be inquired about dyspnoea (none, mild, moderate or severe).

Postoperative pulmonary complications may be correlated with the initial lung inflammatory response and will be recorded during the first postoperative week: [atelectasis, pneumonia, respiratory failure, reintubation, acute respiratory distress syndrome (ARDS), pleural effusion, pneumothorax, bronchospasm], as well as cardiological complications, surgical haemorrhage, acute kidney injury, length of stay in the ICU, length of hospital stay, reoperation during the first 14 days, readmission in the ICU during the first 14 days, readmission in the hospital during the first 30 days and mortality at 30 and 90 days.

#### **Detailed examinations**

#### -Ultrasound

Lung ultrasound (LUS) will be performed in each participant's dependent and non-dependent lung. Participants will be placed in a semi-recumbent position. Each hemithorax will be divided into 6 areas: anterior, lateral and posterior, separated by the anterior and posterior axillary lines, each divided into upper and lower zones. First, for each zone, subcutaneous emphysema (no emphysema, mild or moderate) and the feasibility of ultrasound evaluation (feasible, non-feasible) will be deemed. The focus will be set just below the pleural line. For each echographic examination, the most pathological area will be evaluated. The pleural line will be assessed for mobility (no mobility, lung pulse or lung sliding) and shape (regular or irregular). Specifically, the pleural line will be checked on the 2nd and 3rd intercostal space to assess the presence and extent of pneumothorax. B-lines will be counted (0-10) and lung consolidations (none, subpleural, translobar) will be looked for. A semiquantitative score, the modified lung ultrasound score (mLUSS), will be calculated for each hemithorax to assess lung aeration at each time point. The presence and size of pleural effusion will also be assessed in the most dependent region for each hemithorax. Cineloops will be stored and analysed offline by another independent and blinded anaesthesiologist. The level of agreement for mLUSS will be tested.

Diaphragm thickening fraction will be assessed at the zone of apposition located in the midaxillary line between the eight and tenth ribs in a semi-recumbent position. Thickness will be measured from the inside edge of the diaphragmatic pleura to the inside edge of the peritoneal membrane at the end-expiration (EE) and end-inspiration (EI). The percent change in diaphragmatic thickness will be calculated by ([thickness at EI - Thickness at EE]/Thickness at EE).

Hand-held echocardiography will be performed. Feasibility will be deemed (feasible, non-feasible). Ejection fraction of the left ventricle will be visually assessed (normal function, mild or moderate dysfunction). Left heart preload and diastolic function will be evaluated with the following parameters: E wave, A wave, E/A, e' wave, E/e' and lateral S' wave. Right heart systolic function will be evaluated with lateral S' wave.

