# **Detailed description**

Postoperative pulmonary complications (PPC) are common after lung resection surgery, with an incidence that ranges between 11-32%. As PPC are associated with worse outcomes, many studies aim to find predictors that identify high risk patients and prompt specific interventions and/or monitoring and hence, improve outcomes. PPC result from lung injury inherent to lung resection surgery. Lung aeration changes seen with lung ultrasound (LUS) could detect lung injury and thus, identify patients at high risk of PPC. The underlying mechanisms of lung injury are different in the dependent and non-dependent lung; oxidative stress in both lungs, lung injury associated with one-lung ventilation in the dependent lung and ischemia/reperfusion or surgical manipulation in the non-dependent lung. LUS evaluates the dependent and non-dependent lung separately and so it can be valuable in understanding the characteristics and intensity of lung injury in each lung specifically.

This is a prospective, single-centre, observational study in which 30 consecutive participants with non-small cell lung cancer scheduled for lung resection via VATS will be recruited. Participants will be divided in two groups depending on the size of the resection. First group will be resection less than lobectomy. Second group will be resection equal to or greater than lobectomy. Participants will be recruited consecutively until there are 15 patients in each group. LUS will be performed in each participant's operated and non-operated lung at three predefined time points: before surgery, after extubation and 24 h after surgery. Each hemithorax will be divided into 6 areas: anterior, lateral and posterior, separated by the anterior and posterior axillary lines, each divided into upper and lower zones. For each echographic examination, cineloops of the most pathological findings in each area will be stored and analysed offline by two independent and blinded anaesthesiologists. From these, a semiquantitative score, the modified lung ultrasound score (mLUSS), will be calculated for each hemithorax to assess lung aeration at each time point. The level of agreement for mLUSS will be tested. At the same predefined time points blood plasma samples will be collected, flash-frozen and stored in order to measure levels of the inflammatory mediators IL-6, IL-10 and TNF $\alpha$ .

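### The ultrasound section's rule on which area is evaluated conflicts with the per-area rule in the Detailed description and, read literally, would not span the 0-36 primary score

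*Protocol*

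**What the plan says.** Four statements in the Protocol bear on which parts of the lung enter the primary score.

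- **Primary outcome measure:** "the modified lung ultrasound score (mLUSS) ranges 0-36", compared across the preoperative, immediate postoperative and 24-hour time points.
- **Detailed description:** each hemithorax has six areas, and "For each echographic examination, cineloops of the most pathological findings in each area will be stored and analysed offline by two independent and blinded anaesthesiologists". The mLUSS of each hemithorax is derived from these loops.
- **Detailed examinations, Ultrasound, layout and first step:** "Each hemithorax will be divided into 6 areas: anterior, lateral and posterior, separated by the anterior and posterior axillary lines", with an upper and lower part to each. Then: "First, for each zone, subcutaneous emphysema (no emphysema, mild or moderate) and the feasibility of ultrasound evaluation (feasible, non-feasible) will be deemed".
- **Same section, next steps:** "For each echographic examination, the most pathological area will be evaluated". Pleural line, B-lines and consolidations follow, with no further mention of doing this zone by zone. The section then says: "A semiquantitative score, the modified lung ultrasound score (mLUSS), will be calculated for each hemithorax to assess lung aeration at each time point".

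The sections on the preoperative evaluation, the immediate postoperative period and the 24-hour assessment all send the reader to the end of the document for how examinations are done. The Ultrasound section is therefore the working instruction.

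**The concern.** Two sentences that open with the same phrase give different selection rules. One takes the worst finding inside every area; the other takes the worst area.

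An operator who followed the Ultrasound section to the letter would describe the pleural line, B-lines and consolidations in the worst area and leave the others undescribed. Two things would follow. The score would be a worst-area value and not a sum over the lung. And because the worst area can move between time points, a change in mLUSS could compare different places.

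The primary outcome depends on this sentence, and so does the first secondary outcome, the ultrasound findings in each lung.

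**Working it through.** **Inputs**

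- Areas per hemithorax: 6 (Detailed description; Ultrasound).
- Hemithoraces: 2.
- Range of the primary score: 0 to 36 (Primary outcome measure).
- Points per area: not stated. Equal points per area are assumed below.

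**Step 1. Reproduce the stated range.** Number of areas = 6 × 2 = 12. Points per area needed to reach the stated maximum = 36 / 12 = 3. With 0 to 3 points in every area, each hemithorax runs 0 to 18 and both lungs together 0 to 36, as stated. Other per-area maxima over 12 areas miss it: 2 points give 24, 4 give 48 and 6 give 72. The stated range therefore fits the rule in the Detailed description, with every area scored.

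**Step 2. Apply the Ultrasound sentence literally.** A score is calculated for each hemithorax, so at least one area per side must be scored. With one area per side at 3 points, the maximum = 2 × 3 = 6, which is 6/36 = 1/6 of the range. The other 12 − 2 = 10 areas would have no B-line or consolidation data.

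**Step 3. Sensitivity to the assumption.** With *m* points in every area, the full score is 12*m* and the worst-area score 2*m*, so the fraction is 2*m* / 12*m* = 1/6 whatever *m* is. If 36 instead described a single hemithorax, 36 / 6 = 6 points per area, and one area would again carry 6/36 = 1/6. To reach 36 from one area per side, each would need 36 / 2 = 18 points. The fraction depends on equal weights, not on the value 3.

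**Step 4. Can the two sentences mean the same thing?**

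| Feature of the text | One area per side | Every area |
|---|---|---|
| In the Detailed description an examination contains several areas, and the Ultrasound section reuses the phrase | supports | |
| The Ultrasound section has just used the word area for the six sectors | supports | |
| Zone-by-zone wording is used for emphysema and feasibility but not for B-lines and consolidations | supports | |
| Feasibility is judged in every zone, which has little purpose if one area is scored | | supports |
| The stated range of 0 to 36 | | supports |
| The explicit per-area loops in the Detailed description | | supports |

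The literal wording favours one area. The purpose of the surrounding text, the stated range and the other section favour all areas.

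**The case against.** A reader might infer that the Ultrasound section restricts scoring to a single area and so makes the primary score impossible. The documents do not support that:

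- The sentence does not exclude the other areas.
- One area per two-lung scan (3 of 36 under the same assumption) does not fit the paragraph, because it calculates a score for each hemithorax.
- The vocabulary is loose. The same six units are called both areas and zones, and an echographic examination is not defined. It could mean the scan of one zone, and the sentence would then ask for the worst spot within that zone, in agreement with the Detailed description.
- Where one reading reconciles every section and the other makes the stated range unreachable, the first is the natural one.

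Most of this stands. It shows what was probably intended and rules out calling this a deliberate worst-area design. It does not make the sentence correct. In the Detailed description an examination plainly spans several areas, so the reconciling reading needs the same phrase to change meaning between sections. If all areas are meant, the section that operators are sent to does not say so.

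**Conclusion.** The point holds as an inconsistency in the acquisition rule for the primary outcome. The Ultrasound sentence conflicts with the Detailed description. Read literally it allows at most one area per hemithorax, about 6 of 36 points if the points are spread equally over the areas, and it lets the scored place change between time points.

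Both consequences depend on someone following the literal reading; nothing in the Protocol shows that this was planned or has happened. The 6 of 36 figure also rests on equal points per area, which the Protocol does not give.

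The correction is worth making because the sentence governs data collection. If areas are not recorded, no analysis plan can restore them.

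**What to change.** Replace the sentence in the Ultrasound section with wording such as:

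> In every area of each hemithorax (6 per side) that is feasible to examine, the most pathological finding will be recorded, stored as a cineloop and scored, at every time point. Areas that are not feasible will be recorded as such.

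This brings the section into line with the Detailed description and the 0 to 36 range. The second part is needed because the section itself expects that some zones cannot be examined, so an unconditional promise to score all 12 would not be kept. How non-feasible areas enter the score is a separate matter that this sentence does not settle.

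The cost is one sentence in the Protocol, plus the same wording wherever the scans are recorded. No procedure is added, since per-area loops are already foreseen. If scans have already been taken, check that the stored loops cover every feasible area; those that do can still be scored offline.
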